#### **7.1.1.3 Intensity**

**Intensity** of all adverse events will be graded according to the NCI Common Terminology Criteria for Adverse Events v 4.03 (CTCAE) on a five-point scale (grades 1 to 5) and all grade 3 and above will be reported in detail on the eCRF. Adverse events not listed on the CTCAE should be graded as follows:

**Table 7.1 CTC AE version 4.03 adverse event grading**

CTC Grade	Equivalent To:	Definition
Grade 1	Mild	Discomfort noticed but no disruption of normal daily activity
Grade 2	Moderate	Discomfort sufficient to reduce or affect daily activity; no treatment or medical intervention is indicated although this could improve the overall well-being or symptoms of the patient
Grade 3	Severe	Inability to work or perform normal daily activity; treatment or medical intervention is indicated in order to improve the overall well-being or symptoms; delaying the onset of treatment is not putting the survival of the patient at direct risk.
Grade 4	Life threatening/ disabling	An immediate threat to life or leading to a permanent mental or physical conditions that prevents work or performing normal daily activities; treatment or medical intervention is required in order to maintain survival.
Grade 5	Death	AE resulting in death

#### 7.1.1.4 Drug-Adverse Event relationship

The causality relationship of study drug to the adverse event will be assessed by the investigator as either:

**Yes or No**

If there is a reasonable suspected causal relationship to the study medication, i.e. there are facts (evidence) or arguments to suggest a causal relationship, drug-event relationship should be assessed as **Yes**. In other studies, the terms that qualify for a “Yes” assignation include “Definite”, “Probable”, or “Possible”.

The following criteria should be considered in order to assess the relationship as **Yes**:

- Reasonable temporal association with drug administration
- Known response pattern to suspected drug
- Disappears or decreases on cessation or reduction in dose
- Reappears on rechallenge.

The following criteria should be considered in order to assess the relationship as No; in other studies, the terms that qualify for a “No” assignation include “Unlikely”, or “Unrelated”:

- It does not follow a reasonable temporal sequence from administration of the drug
- It may readily have been produced by the subject’s clinical state, environmental or toxic factors, or other modes of therapy administered to the subject
- It does not follow a known pattern of response to the suspected drug
- It does not reappear or worsen when the drug is re-administered.

#### **7.1.1.5 Definition of Serious Adverse Events**

A serious adverse event is any experience that suggests a significant hazard, contraindication, side effect or precaution. It is any Adverse Event that at any dose fulfils at least one of the following criteria:

- Is fatal; (results in death; NOTE: death is an outcome, not an event)
- Is Life-Threatening (NOTE: the term "Life-Threatening" refers to an event in which the patient was at immediate risk of death at the time of the event; it does not refer to an event which could hypothetically have caused a death had it been more severe)
- Requires in-patient hospitalization or prolongation of existing hospitalization
- Results in persistent or significant disability/incapacity
- Is a congenital anomaly/birth defect
- Is medically significant or requires intervention to prevent one or other of the outcomes listed above.

#### **7.1.1.6 Progression of Underlying Malignancy**

Progression of underlying malignancy is not reported as an adverse event if it is clearly consistent with the suspected progression of the underlying cancer as defined by RECIST 1.1. Hospitalization due solely to the progression of underlying malignancy should NOT be reported as a serious adverse event. Clinical symptoms of progression may be reported as adverse events if the symptom cannot be determined as exclusively due to the progression of the underlying malignancy, or does not fit the expected pattern of progression for the disease under study.

Symptomatic deterioration may occur in some patients. In this situation, progression is evident in the patient’s clinical symptoms, but is not supported by the tumor measurements. Or, the disease progression is so evident that the investigator may elect not to perform further disease assessments. In such cases, the determination of clinical progression is based on

symptomatic deterioration. These determinations should be a rare exception as every effort should be made to document the objective progression of underlying malignancy.

If there is any uncertainty about an adverse event being due only to the disease under study, it should be reported as an AE or SAE.

### 7.1.2 Treatment and Follow-up AEs

After the discontinuation of therapy with regorafenib continue to follow up AEs as follows:

**Related AEs:** Follow until one of the following occurs:

- Resolved or improved to baseline
- Relationship is reassessed as unrelated
- Start of new anti-cancer regimen
- Investigator confirms that no further improvement can be expected
- Clinical or safety data will no longer be collected, or final database closure
- Death.

**Unrelated severe or life threatening AEs:** Follow until one of the following occurs:

- Resolved or improved to baseline
- Severity improved to grade 2
- Start of new anti-cancer regimen
- Investigator confirms that no further improvement can be expected
- Clinical or safety data will no longer be collected, or final database closure
- Death.

The final outcome of each adverse event must be recorded on the CRF.

**Unrelated Grade 1 or Grade 2 AEs:** Follow as clinically indicated

### 7.1.3 Laboratory Test Abnormalities

Any laboratory result abnormality fulfilling the criteria for a serious adverse event (SAE) should be reported as such.

Any treatment-emergent abnormal laboratory result that is clinically significant, i.e., meeting one or more of the following conditions, should be recorded on the adverse event eCRF:

- Accompanied by clinical symptoms
- Leading to a change in study medication (e.g. dose modification, interruption or permanent discontinuation)
- Requiring a change in concomitant therapy (e.g. addition of, interruption of, discontinuation of, or any other change in a concomitant medication,

therapy or treatment).

#### **7.1.4 Follow-up of Abnormal Laboratory Test**

In the event of medically significant unexplained abnormal laboratory test values, the test should be repeated and followed until it has returned to the normal range, baseline value and/or an adequate explanation of the abnormality is found. If a clear explanation is established it should be recorded in the eCRF.

### **7.2 Handling of Safety Parameters**

#### **7.2.1 Reporting of Adverse Events**

**All adverse events (related and unrelated) Grade 3 or worse** occurring during the study and up to 30 days after the last dose of study medication must be reported. Reporting the specific time of onset of a given AE is only necessary when it occurs in relation to study drug administration.

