#### **4.3 Treatment assignment**

Eligible patients will be registered by the site personnel and randomized at time of registration by the SARC operations office. For patients on substudies requiring randomization, subjects will be randomly assigned to receive either regorafenib 160 mg once daily or placebo (1:1), 3 weeks on, 1 week off.

Patients, investigators who give the treatment, those assessing outcomes, and those who will perform outcome analyses are blinded as to the allocation. Treatment allocation will remain masked until the time of disease progression, at which time assignment will be unblinded, so that patients on placebo may be crossed over to active treatment.

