### **5. TREATMENT PLAN**

#### **5.1 Agent Administration**

**Cohorts A and B:** patients with liposarcoma or osteosarcoma will be randomized 1:1 to receive regorafenib or placebo. Crossover of the placebo group is permitted if patients still meet all entry criteria to continue on treatment. (Accrual completed as of amendment 5)

**Cohort C:** patients with Ewing sarcomas will all receive regorafenib from the start of the study. (Accrual completed as of amendment 5)

**Cohort D:** patients with rhabdomyosarcoma (fusion-positive alveolar, embryonal, and fusion-negative alveolar) will all receive regorafenib from the start of the study

**Cohort E:** patients with mesenchymal chondrosarcoma will all receive regorafenib from the start of the study

In all cases the length of one cycle of therapy is 28 days (3 weeks on, 1 week off). If a patient experiences toxicity and is not due to resume therapy until the 1 week of the cycle off treatment, the subsequent cycle of therapy may start after a minimum of 1 week off regorafenib.

Example 1: A patient experiences toxicity at the day 8 visit of a cycle and treatment is held until day 15. After resuming treatment from day 15 until day 22, the patient is off treatment from days 22-28, and starts again on day 29, which is day 1 of the new cycle of therapy.

Example 2: A patient experiences toxicity at day 17 and treatment is held through day 24, which is after the expected end of treatment that cycle on day 22. The patient may resume therapy with a new cycle of therapy as early as day 25, or may stay off therapy through day 28, resuming treatment cycle day 29/day 1 of the new cycle.

Conversely, imaging studies will be performed as outlined in the protocol and no changes in the scheduled scans are permitted. However, patients with clinical deterioration may have imaging studies earlier than scheduled, which may take the patient off study earlier than expected.

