#### **7.2.2 Reporting of Serious Adverse Events (immediately reportable)**

Any clinical adverse event or abnormal laboratory test value that is *serious* and which occurs during the course of the study (as defined in section 7.1 above), regardless of the treatment arm, must be reported to SARC **within 24 hours** of the Principal Investigator becoming aware of the event (expedited reporting). SARC will then forward MedWatch data form(s) to the overall study PI and Cohort Principal Investigators and the supporter upon receipt. If only limited information is initially available, follow-up reports are required. The original SAE Form must be kept on file at the study site.

SAEs must be reported on the MedWatch Form 3500A along with the completed Fax Coversheet and faxed or sent electronically to SARC as listed. (See **Appendix B**).

Related Serious Adverse Events **MUST** be collected and reported regardless of the time elapsed from the last study drug administration, even if the study has been closed.

Unrelated Serious Adverse Events must be collected and reported during the study and for up to 30 days after the last dose of study medication.

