#### **12.1.2 Safety variables**

A treatment-associated adverse event (TAAE) is defined as an AE that was not present at baseline, or an exacerbation of a pre-existing AE. For laboratory data, a treatment-associated abnormal laboratory value (TAAV) represents an abnormal value that was normal at baseline.

Safety variables of analysis include the following:

- Proportions of patients with any TAAEs
- Proportions of patients with serious TAAEs
- Proportions of patients with Grade 3 or greater TAAEs
- Proportions of patients with severe TAAE
- Proportions of patients with TAAEs leading to study drug discontinuation
- Proportions of patients with TAAEs leading to dose modifications
- Proportions of patients with drug-related TAAEs
- Proportions of patients with TAAVs
- Mean and median changes from baseline in vital signs
- Mean and median changes from baseline in clinical laboratory measures
- Mean and median changes from baseline in measures from electrocardiography.

It is noted that patients who cross over from placebo to receive open-label regorafenib will have treatment-related derivations from first dose of placebo during the double-blind period and treatment-related derivations from first dose of regorafenib during the open-label portion of the study.

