## **12.5 Analysis of Secondary Endpoints**

Descriptive statistics will be generated for secondary endpoint variables.

Methodologies for variables that are proportions will include construction of confidence intervals for each group and for the difference between groups. For example, a Fisher exact test will be used for single-population analyses, while a Mantel-Haenszel test will be used for analyses combining data across strata.

Methodologies for time-to-event variables will include construction of 95% confidence intervals for each group separately and for the difference between groups. For analysis, a log-rank test will be used. Logistic regression and analysis of covariance methods on measured variables with baseline measures as covariables. Kaplan Meier curves will be displayed for time-to-event data.

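### Cohorts A and B: adverse-event proportions are compared between arms without a common end to the randomized safety period, so crossover can bias the comparison in either direction

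*Combined protocol and SAP*

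**What the plan says.** Incidence of adverse events is a secondary objective for all cohorts (section 1.2). Five parts of the protocol bear on how it is compared in the two randomized cohorts.

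- **Reporting window (7.2.1).** Grade 3 or worse events "occurring during the study and up to 30 days after the last dose of study medication must be reported". The wording is the same for both arms. Under 7.2.2, serious events judged related must "be collected and reported regardless of the time elapsed from the last study drug administration", while unrelated ones are collected to 30 days.
- **Unblinding (4.3).** "Treatment allocation will remain masked until the time of disease progression, at which time assignment will be unblinded", so that placebo patients can move to active drug.
- **Crossover (5.1).** "Crossover of the placebo group is permitted if patients still meet all entry criteria to continue on treatment". Only placebo patients have this option. No interval between the last placebo dose and the first open-label dose is given.
- **Safety derivations (12.1.2).** The section notes that "patients who cross over from placebo to receive open-label regorafenib will have treatment-related derivations from first dose of placebo during the double-blind period", and a second set from the first open-label regorafenib dose. It gives two starting points and no end point. The definition of a treatment-associated event has no end date either.
- **Comparison (12.5).** For proportions the plan calls for "construction of confidence intervals for each group and for the difference between groups". It does not mention exposure adjustment.

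**The concern.** A between-arm difference in the proportion of patients with an event is interpretable only if both arms are observed under the same rule. Here one arm has a possible boundary, the start of open-label drug, that the other arm cannot have.

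Two readings are available, and they push in opposite directions. If the first open-label dose closes the placebo record, a regorafenib patient who stops keeps up to 30 days that a crossed-over placebo patient loses, and regorafenib looks worse than it is. If every event within 30 days of the last placebo dose stays with placebo, toxicity from the first weeks of open-label regorafenib is counted against placebo, and regorafenib looks better than it is.

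The placebo comparison is the only controlled safety evidence this trial yields in liposarcoma and osteosarcoma, so its rule should be fixed in advance.

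**Working it through.** **Check of the planning inputs.** The protocol gives no figure for safety time at risk. The PFS design in 12.2 supplies the durations, so I reproduced that first. With hazard ratio 0.4, one-sided 5%, 90% power and 1:1 allocation, events = 4 × (1.645 + 1.282)² / (ln 0.4)² = 40.8, that is 41. The protocol states 42, at which power is 0.907. The inputs are consistent.

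**Inputs for the illustration**

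- Time on randomized treatment: exponential with the planned PFS medians of 2 months (placebo) and 5 months (regorafenib), from 12.2. Means are 2/ln 2 = 2.885 and 5/ln 2 = 7.213 months.
- Tail w = 30/30.4375 = 0.986 month (7.2.1).
- Crossover share c = 85%: an assumption. It is the placebo share the protocol quotes for the GIST phase III trial (2.4.2). None is given for this trial.
- Background Grade 3+ rate λ, equal in both arms: assumed 0.02 to 0.20 per month.
- Gap from last placebo dose to first open-label dose: not stated; 0, 14 and 28 days used.

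**Formula.** With μ = ln 2/median, the proportion with at least one event is P(w) = 1 − [μ/(μ+λ)] × exp(−λw). If crossover closes the record after a gap g, the placebo proportion is c × P(g) + (1 − c) × P(w).

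**Reading 1: placebo record closed at the first open-label dose (c = 85%)**

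| λ per month | Full 30-day window | Closed, no gap | Shortfall, no gap | Shortfall, 14-day gap |
|---|---|---|---|---|
| 0.02 | 7.3% | 5.7% | 1.6 points | 0.8 |
| 0.05 | 16.8% | 13.2% | 3.6 | 1.9 |
| 0.10 | 29.7% | 23.5% | 6.2 | 3.2 |
| 0.20 | 47.9% | 38.3% | 9.6 | 4.9 |

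At λ = 0.10 and no gap, μ/(μ+λ) = 0.3466/0.4466 = 0.776, so the shortfall is 0.85 × 0.776 × (1 − 0.906) = 6.2 points. With a 28-day gap (0.920 month) it is 0.85 × 0.776 × (0.912 − 0.906) = 0.4 points. With no gap, 50% crossover gives 3.6 points and 100% gives 7.3.

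**Reading 2: all events within 30 days of the last placebo dose stay with placebo.** Take λ = 0.10, c = 85%, immediate crossover and an assumed 20% to 40% chance of Grade 3+ drug toxicity in the first 30 days of regorafenib. The placebo proportion is 0.85 × [1 − 0.703 × (1 − p)] + 0.15 × 0.297, which is 41.6% at p = 0.20 and 53.6% at p = 0.40, against 29.7% without the misattribution.

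**Unequal treatment time, no drug effect, λ = 0.10**

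| Window | Mean months at risk, regorafenib / placebo | Ratio | Proportions | Difference |
|---|---|---|---|---|
| 30-day tail in both arms | 8.20 / 3.87 | 2.12 | 47.4% vs 29.7% | 17.7 points |
| Reading 1, no gap, 85% crossover | 8.20 / 3.03 | 2.70 | 47.4% vs 23.5% | 23.9 points |
| Both arms cut at end of blinded treatment | 7.21 / 2.89 | 2.50 | 41.9% vs 22.4% | 19.5 points |

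The last row shows that a common cut-off does not by itself make crude proportions comparable. Rates per unit of time at risk on that window would recover the same λ in both arms under this model.

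**The case against.** The best defence is that the protocol nowhere says the placebo window is cut. The 30-day rule in 7.2.1 is a reporting duty worded identically for both arms, and 12.1.2 names starting points only. Since 4.3 does not limit unblinding at progression to placebo patients, a double-blind period could be taken to end there in both arms, with no asymmetry. This stands as far as it goes: the cut-off is an inference. But the protocol does not adopt that symmetric reading either, and the two readings worked through above give opposite biases.

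The 6-point figure is also near the top of what is plausible at that event rate. Scheduled week-8 imaging falls in the off week (9.2), so part of the tail has usually passed before progression is declared. Crossover then requires the entry criteria to be met again, including laboratory tests; 3.2.8 has a 14-day interval after prior therapy whose application to placebo is not stated. A delay of two to four weeks leaves about 3 points down to under 1.

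With about 24 patients per arm, 6 points is 1.5 patients, and the 95% half-width for 29.7% against 23.5% is 1.96 × √(0.297 × 0.703/24 + 0.235 × 0.765/24), about 25 points. Safety is a descriptive secondary objective. These facts limit the consequence. They do not supply the missing rule, which costs little to write.

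**Conclusion.** The between-arm safety comparison in Cohorts A and B is not fully defined. As 12.1.2 is most naturally read, it understates the placebo proportion by about 6 points with immediate crossover, 3 points at 14 days and under 1 point at 28 days, assuming 0.10 events per month and 85% crossover. With no gap, the range is 1.6 to 9.6 points for 0.02 to 0.20 events per month. The literal 30-day reading reverses the sign. Either effect sits on top of the larger distortion from unequal treatment time, 17.7 points at the planned medians and 0.10 per month. The event rate, crossover share, gap and early-toxicity probability are all assumptions.

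Three stronger readings are tempting and are not supported:

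- **That the plan is certainly biased against regorafenib.** This needs a cut-off the text does not state.
- **That the lost month matters more because events cluster after progression.** Section 11.1.5 has signs and symptoms of progression reported as serious events, but 7.1.1.6 keeps clear progression, and hospitalization due solely to it, out of adverse-event reporting. The documents give no rate for that period.
- **That open-ended collection of related serious events in 7.2.2 inflates the regorafenib arm.** That duty applies regardless of arm, and nothing says late related events enter a between-arm proportion.

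This is a worthwhile, cheap improvement to the analysis, not a threat to the primary PFS result.

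**What to change.** In 12.1.2, define one window for every between-arm safety comparison in Cohorts A and B. It should run from the first blinded dose to a cut-off applied identically in both arms and ending before crossover: the date of progression or unblinding, or the last blinded dose if earlier. A window closed at the first open-label dose would not do, because only placebo patients have such a date.

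On that window, report exposure-adjusted incidence rates or the cumulative incidence of time to first event alongside the crude proportions. Without this the treatment-time imbalance remains. Put the 30-day tail, late related serious events and open-label events in separate, non-comparative tables. Leave the reporting duties in 7.2 unchanged.

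The cost is one derivation rule and the added tables. Accrual to both cohorts is complete (5.1), so an analysis rule is the correction still available. There are two drawbacks. Delayed regorafenib events after stopping leave the comparative table and must be read from the separate one. Onset dates must also be on file to apply the cut-off, which should be checked because 7.2.1 says: "Reporting the specific time of onset of a given AE is only necessary when it occurs in relation to study drug administration".

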#### **7.2.2 Reporting of Serious Adverse Events (immediately reportable)**

Any clinical adverse event or abnormal laboratory test value that is *serious* and which occurs during the course of the study (as defined in section 7.1 above), regardless of the treatment arm, must be reported to SARC **within 24 hours** of the Principal Investigator becoming aware of the event (expedited reporting). SARC will then forward MedWatch data form(s) to the overall study PI and Cohort Principal Investigators and the supporter upon receipt. If only limited information is initially available, follow-up reports are required. The original SAE Form must be kept on file at the study site.

SAEs must be reported on the MedWatch Form 3500A along with the completed Fax Coversheet and faxed or sent electronically to SARC as listed. (See **Appendix B**).

Related Serious Adverse Events **MUST** be collected and reported regardless of the time elapsed from the last study drug administration, even if the study has been closed.

Unrelated Serious Adverse Events must be collected and reported during the study and for up to 30 days after the last dose of study medication.

